### 3.3.2 Randomisation and Blinding Procedures

#### *Randomisation and Blinded Treatment Allocation*

Patients will be randomised in a 1:1:1:1 ratio to JTA-004 groups or Reference group [REDACTED] [REDACTED] according to a randomisation scheme through Interactive Web Response System

**JTA- KOA1 - Clinical Study Protocol**

JTA-KOA1-CSP	V 04	Author: EB	Date: May 10, 2017	Pg. 36/114
--------------	------	------------	--------------------	------------

(IWRS). The IWRS will only be accessible through a secure website to authorised users with valid login and password.

Once the eligibility and participation of the patient has been confirmed:

- The IWRS will determine the treatment group of the patient and allocate a treatment number to the patient in order to associate a specific treatment (IMP or Reference) to a specific patient.
- A notification of the treatment number without reference to the nature of the treatment (blinded notification) will be sent to the Principal Investigator and Sponsor's representative.
- A notification of the treatment number with the nature of the treatment (unblinded notification) will be sent to the Sponsor's Production Manager in order to label the treatment with the treatment number but also to the local Pharmacist and the Independent Physician.

*Treatment Preparation, Patient Treatment and Blinding of the Study*

Not later than the day before the treatment Visit #2, the kit containing the treatment (IMP or reference product) labelled with the treatment number will be shipped to the Hospital Pharmacy. The IMP will be reconstituted by the pharmacist of the hospital at the request of the Independent Physician. The reference product does not need reconstitution but the Independent Physician must also require the preparation by the local. Before the injection time, the Study Nurse will pick up the reconstituted IMP or the reference product at the Hospital Pharmacy and bring it, into a blinding transfer box, to the Independent Physician.

Although shipping packages will be identical, JTA-004 and reference products will not be provided in the same primary packaging.

The study will be conducted double-blind with reference to the evaluation of trial results.

- The Investigators will be blind to treatment assignments with respect to the patient evaluation. They will recruit, include and assess patients during the whole study follow-up period, but will not treat the patients. Investigators will therefore not be aware of treatment assignment.

**JTA- KOA1 - Clinical Study Protocol**

JTA-KOA1-CSP	V 04	Author: EB	Date: May 10, 2017	Pg. 37/114
--------------	------	------------	--------------------	------------

- Patients will be blind to treatment assignment, as the four patient groups will undergo the same intra-articular injection (performed by the Independent Physician). As the appearance of the resuspended JTA-004 is different from the reference, appropriate measures must be taken to ensure that the patient is unable to see the injected treatment during the injection procedure. The injection procedure will be identical in all patients.
- Only the Independent Physician and the local Pharmacist will not be blind to treatment assignments, as they will perform the reconstitution or the intra-articular administration of the IMP.

Unblinding is restricted to emergency situations and should only be used under circumstances in which knowledge of the treatment given during the trial is necessary for the proper treatment and medical care of the patient. In the case of medical emergency, decoding will be done for a patient by choosing the “Unblinding” option of the IWRS that allows the user to learn the nature of the treatment taken by a patient in. Under normal circumstances, this option is only available to Principal Investigators/Co-Investigators. In addition, the date of unblinding must be recorded in the appropriate place in the eCRF and signed by the Principal Investigator.

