### 3.3.3 Procedures per Treatment Group

Patients will undergo during Baseline/Treatment visit (Visit #2) a single 2 ml or 4 ml IA administration of JTA-004 or 6 ml of reference treatment into the knee joint. The recommended needle size is a 21-gauge needle (or alternatively a 19-gauge needle) but the choice of the needle size is at the Independent Physician’s discretion. The size of the needle must be recorded in the appropriate place in the eCRF.

After administration, the patient will be asked to remain at the Investigation Site for 45 minutes. For more information regarding the administration procedure of investigational medicinal products, please refer to Section 6 of this protocol.

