#### 6.2.2 Injection Procedure

[REDACTED]

[REDACTED]

JTA-KOA1 - Clinical Study Protocol

JTA-KOA1-CSP

V 04

Author: EB

Date: May 10, 2017

Pg. 53/114

[REDACTED]

[REDACTED]. The injection is accomplished following puncture through the skin and into the joint space. If resistance is encountered, redirection of the needle may be necessary. The use of local anaesthesia with lidocaine prior to the IA injection is at the discretion of the Independent Physician.

The injections will be performed by an Independent Physician who are very well experienced with this type of administration to limit the risk of periarticular administration. Products should be injected in the synovial space only and not into blood vessels, extra-articularly, or in the synovial tissue or capsule. If the whole volume of Investigation Medicinal Product cannot be injected, the reason must be documented in the eCRF.

The products are intended for single use and strict aseptic administration technique must be followed. For the reference, the syringe containing the HA solution should be used immediately [REDACTED] in order to guaranteed the sterility of the product.

If effusion is found in the knee upon needle placement in the joint space, it must be removed before lidocaine and JTA-004 or reference product is injected. [REDACTED]

[REDACTED]

The administration procedure is summarised in the Table 2 below:

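### Section 3.3.2 promises an identical injection procedure, but needle gauge and lidocaine are left to a physician who knows the arm, so these choices can depend on it and blur the comparison of local adverse events

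*Combined protocol and SAP*

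**What the plan says.** Section 3.3.2 (Randomisation and Blinding Procedures) explains patient blinding by saying that all four groups get the same injection. It adds, because the products look different, that "appropriate measures must be taken to ensure that the patient is unable to see the injected treatment during the injection procedure", and closes: "The injection procedure will be identical in all patients".

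Two later sections give choices to the person injecting:

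- Needle gauge, Section 3.3.3: "The recommended needle size is a 21-gauge needle (or alternatively a 19-gauge needle) but the choice of the needle size is at the"; the sentence ends by leaving this to the judgement of the person who injects. The size used goes into the eCRF.
- Local anaesthetic, Section 6.2.2: "The use of local anaesthesia with lidocaine prior to the IA injection is at the discretion of the Independent Physician".

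That person is not blinded. Section 3.3.2 sends the unblinded notification to the sponsor's production manager, "but also to the local Pharmacist and the Independent Physician". It then states: "Only the Independent Physician and the local Pharmacist will not be blind to treatment assignments". The Independent Physician also requests preparation of the product from the pharmacy.

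The injected volume differs by design. Section 3.3.3 describes "a single 2 ml or 4 ml IA administration of JTA-004 or 6 ml of reference treatment into the knee joint".

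**The concern.** A procedure is not identical in all patients if two of its controllable steps are chosen patient by patient. That would matter little if the operator were blind. Here the operator knows the arm, so gauge or lidocaine use could follow it.

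The exposed outcome is local AEs. The protocol expects them from both sources. Section 2.4 lists injection-site pain and joint swelling as effects of hyaluronic acid products, Section 6.2.3 says the procedure itself may cause pain, and Section 8.3 speaks of events from the product or from the procedures. Section 10.7.7 compares AE frequencies between groups with a chi-square or Fisher's exact test. If gauge or lidocaine tracked the arm, that comparison would mix product and procedure.

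**Working it through.** **1. The sentences side by side.** Section 3.3.2 states uniformity without exception. Sections 3.3.3 and 6.2.2 grant discretion without condition. Neither discretion sentence says that the choice must be made before allocation is disclosed or be the same whichever product is given. The volumes (2, 4 or 6 ml) already rule out a literal reading of identical, so the word can only cover the steps a site controls. Gauge and anaesthetic are two of these.

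**2. What the operator knows, and when.** Section 3.3.2 has the kit delivered in advance: "Not later than the day before the treatment Visit #2, the kit containing the treatment" is shipped to the hospital pharmacy. The unblinded notification and the preparation request also come before the injection. An arm-dependent choice is therefore possible. The text does not say when gauge or lidocaine is decided, and a standing personal practice that ignores the arm fits it equally well.

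**3. Why an arm-related choice is plausible.** The arms differ in volume (Section 3.3.3), appearance (Section 3.3.2) and container: vial for JTA-004, ready-to-use syringe for the reference (Table 3). The reference syringe comes without a needle (Section 6.5), so one must be selected. This makes a difference conceivable; it does not show one.

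**4. What is already recorded.** Needle size (Section 3.3.3) and any medication (Section 6.2.4) go into the eCRF. Concomitant medication is a safety variable (Section 10.6) and is summarised (Section 10.7.4). AEs are also tabulated by relationship to product or procedure (Section 10.7.7), but that is a judgement per event and does not show which needle or anaesthetic was used. No readable text commits to a table of gauge by arm.

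**5. Size.** The plan gives no figure for this point. For one option (say, 19-gauge, or lidocaine), the shift in the between-arm difference in an AE rate is

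shift = d × r,

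where d is the between-arm difference in the share of patients given the option and r is the change in AE risk that the option causes. The documents give neither, and r may have either sign.

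The arm size is the plan's own 41 (Section 10.9). It reproduces: a two-sample t-test with 7 mm, SD 10.5 mm, 80% power and two-sided 0.05 gives 36.3, so 37 for analysis, and 37 × 1.10 = 40.7, so 41.

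Purely to show the arithmetic, with both inputs assumed:

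| d | r (points) | shift (points) | patients in 41 |
|---|---|---|---|
| 0.25 | 2 | 0.5 | 0.2 |
| 0.50 | 5 | 2.5 | 1.0 |
| 1.00 | 10 | 10 | 4.1 |

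The last row is extreme. It needs every patient in one arm and none in the other to get the option, and r = 10 points is ten times the 1/100 that Table 8 lists for injection-site pain.

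Expected counts from Table 8 (other hyaluronic acid products) are 41 × 1/10 = 4.1 patients per arm for arthralgia and 41 × 1/100 = 0.41 for injection-site pain. At a 10% rate the standard error of a difference between two arms is √(2 × 0.1 × 0.9 / 41) = 6.6 points, a 95% half-width of 13.0 points. The trial could therefore hardly detect a shift of this kind. That does not make the shift harmless: sampling error does not cancel a systematic difference.

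**The case against.** The strongest reply has four parts.

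- **Context.** The disputed sentence closes the paragraph on patient blinding and describes what the patient goes through. It need not promise that every operator choice is fixed, and one discretion rule applies in all arms. This stands as a reason to call the wording loose. It does not remove the main difficulty, because the person using the discretion knows the arm.
- **Redaction.** Parts of Section 6.2.2, the Visit #2 procedures and Table 1 are blacked out, Section 2.4 refers to separate instructions for use, and Section 10.7.7 leaves safety detail to the SAP. A further rule or table may exist. This stands, so the point rests only on the readable sentences, which carry no condition.
- **Existing safeguards.** Both variables are recorded, and blinded Investigators who do not inject assess the patients. This protects assessment and allows a check afterwards. It does not prevent a difference.
- **Clinical judgement.** An experienced injector should choose needle and anaesthetic, and a gauge that suits a given volume is arguably part of giving that product. That is reasonable, but Section 3.3.2 should then say so instead of stating that the procedure is identical.

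**Conclusion.** The inconsistency is real and minor. Readable text lets an operator who knows the arm choose two co-interventions, while another sentence says that the procedure does not vary. The choices can depend on the arm and could blur the comparison of local, procedure-related AEs. Size and direction are unknown; the table above is illustration and supports no estimate. The rating is minor because the difference is only possible and the outcome affected is a limited set of local AEs, not because a shift would fall within sampling error.

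A reader might infer three stronger things that the documents do not support:

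- *That both choices are made after the arm is known.* The notification and shipping steps show only that they can be.
- *That patients would be unblinded.* The product is hidden from the patient, and nothing links gauge or lidocaine to a patient's guess.
- *That Month 6 WOMAC pain would be biased.* The documents give no effect of either choice on that endpoint, and none is claimed.

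The conclusion assumes that the redacted text contains no rule fixing these choices.

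**What to change.** - **Default before the arm is known.** Each site, or the Independent Physician before seeing the unblinded notification, sets a default needle gauge and lidocaine practice that suits all four treatments and applies whichever is allocated. Which gauge or practice is right remains a clinical matter.
- **Recorded deviations.** Allow a change for any patient-level clinical reason, such as lidocaine allergy, patient request, anatomy, or effusion or resistance at needle placement, and record the reason. The person deviating may still know the arm, but deviations become visible and countable.
- **Wording.** In 3.3.2, say that volume differs by arm and that the other steps follow the default. Align 3.3.3 and 6.2.2.
- **Reporting.** Tabulate gauge, lidocaine use and deviations by arm beside the local AEs.

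Cost: rewording three sections, one declaration, one eCRF field for deviations and their reasons, one table, and slightly less freedom for the operator. Needle size and medication are already collected.

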### 3.3.3 Procedures per Treatment Group

Patients will undergo during Baseline/Treatment visit (Visit #2) a single 2 ml or 4 ml IA administration of JTA-004 or 6 ml of reference treatment into the knee joint. The recommended needle size is a 21-gauge needle (or alternatively a 19-gauge needle) but the choice of the needle size is at the Independent Physician’s discretion. The size of the needle must be recorded in the appropriate place in the eCRF.

After administration, the patient will be asked to remain at the Investigation Site for 45 minutes. For more information regarding the administration procedure of investigational medicinal products, please refer to Section 6 of this protocol.

**JTA- KOA1 - Clinical Study Protocol**

JTA-KOA1-CSP

V 04

Author: EB

Date: May 10, 2017

Pg. 38/114

### 3.4 Patient Evaluation

#### 3.4.1 Clinical Evaluation

In order to avoid bias, (self-reported) clinical evaluation should be the first procedure during a study visit before discussing with the Principal Investigator or the Study Nurse/Coordinator. The patient must complete the questionnaires alone without any outside intervention (Bryant and Fernandes, 2011).

The following clinical assessments will be evaluated:

- WOMAC® VA3.1 (see details in section 5.3.1 and Annex 1): at each follow-up visit from the baseline/treatment visit to the end of the study follow up at Month 6, patients will be assessed using the WOMAC® Index for knee OA severity and symptoms. To this end, each Investigating Site will receive validated WOMAC® Indexes in the language of the patient and the WOMAC® Index User Guide in English.

- █ [REDACTED]
- [REDACTED]

#### 3.4.2 Biological Evaluation

At baseline/treatment, and 3 and 6 months after treatment, the effects of the investigational medicinal products on knee OA severity will also be explored [REDACTED]

[REDACTED] This method may be thus an opportunity to gather more information on the mode of action and efficacy of JTA-004.

**JTA- KOA1 - Clinical Study Protocol**

JTA-KOA1-CSP

V 04

Author: EB

Date: May 10, 2017

Pg. 39/114

### 3.4.3 Radiological Evaluation

The Principal Investigator or the radiologist must grade the severity of OA according to Kellgren-Lawrence Radiographic Score. For the purpose of this study, radiographic assessment is only required on the target knee [REDACTED]

## 3.5 Study Population and Selection

### 3.5.1 Eligibility

Prior to patient inclusion and randomisation, a Screening period is planned to allow verification of patient eligibility.

[REDACTED]

[REDACTED]

- [REDACTED]
- [REDACTED]
- [REDACTED]

There is a random gender distribution in this study. The patients will not be selected according to their gender but according to inclusion and exclusion criteria as set out in this protocol. Since there are no known or expected gender differences in efficacy, and/or safety profile of the study products, no subgroup analysis with gender as a variable is planned.

Once randomised (allocation to either JTA-004 or reference group), patients will receive appointment for the single IA injection.

### 3.5.2 Inclusion Criteria

All patients must satisfy **ALL** the following criteria at study entry:

- Male/female aged between 50 to 79 years.

## JTA- KOA1 - Clinical Study Protocol

JTA-KOA1-CSP	V 04	Author: EB	Date: May 10, 2017	Pg. 40/114
--------------	------	------------	--------------------	------------

- Ambulatory (able to walk unassisted, the use of a crutch or a walking stick is allowed)
- Diagnosed with primary knee OA, fulfilling the following American College of Rheumatology (ACR) criteria at the target knee:
  - Pain  $\geq$  40 mm on a 0-100 mm VAS during the 3 days preceding the date of the Screening Visit (see Annex 2)
  - Morning stiffness not exceeding 30 minutes
  - Kellgren-Lawrence grade II or III (confirmed by X-ray within the last 6 months)
- Insufficient/failed response to analgesics and/or NSAID
- Willing and able to abstain from physical therapy of the knee and knee braces for the entire duration of study
- Capable to understand and comply with study requirements and to provide a written, dated, and signed informed consent prior to any study procedure for participation in the study and transmission of personal "anonymized" data

### 3.5.3 Exclusion Criteria

The following criteria should be checked at the time of study entry. **If ANY exclusion criterion applies, the patient must not be included in the study:**

#### *Current symptoms and/or signs related to the disease under study*

- Isolated symptomatic femoropatellar OA of the target knee
- History of trauma or surgery or arthroscopy at the target knee within 6 months before inclusion
- Concomitant inflammatory disease or other condition affecting the joints (e.g., rheumatoid arthritis, septic arthritis, inflammatory joint disease, metabolic bone disease, psoriasis, gout, microcrystalline arthropathies/chondrocalcinosis, Paget's disease)
- Any musculoskeletal condition (such as hip osteoarthritis, amputation, neurologic disorder) that would impede measurement of efficacy at target knee
- Target knee prosthesis planned within 12 months after the Screening Visit

#### *Current or previous diagnoses, signs and/or symptoms*

**JTA- KOA1 - Clinical Study Protocol**

JTA-KOA1-CSP	V 04	Author: EB	Date: May 10, 2017	Pg. 41/114
--------------	------	------------	--------------------	------------

- Uncontrolled diabetes mellitus, end-stage hepatic or renal disease documented in the patient's file
- Current (or within the last 5 years prior to entering the study) history of solid or haematological neoplasia or bone marrow transplantation (except for basal cell carcinoma and completely excised squamous cell carcinoma)
- Other severe acute or chronic medical or psychiatric conditions or pre-dispositions or laboratory abnormalities, as judged by the Investigator
- Current or past history of coagulation disorders, as judged by the Investigator
- Hypersensitivity to any components of HA-based injection products
- History of hypersensitivity to human biological material including blood and blood derived products, potential excipients and residues from manufacturing process, documented clinically or by laboratory tests
- Hypersensitivity to avian proteins
- Life expectancy less than 6 months

*Current or previous treatment*

- Participation in another clinical study within 6 months prior to Screening
- Patients previously treated with JTA-004
- Treatment:
  - Within 6 months prior to Screening: intra-articular hyaluronic acid injection at the target knee
  - Within 2 months prior to Screening: intra-articular glucocorticoids at the target knee
- Current chemo-, radio- or immuno-cancer-therapy or immunosuppressive therapy
- Current anti-hypertensive medication the effects of which are known to be potentiated by a single dose of clonidine
- Current (or within 6 months prior to Screening) illicit drug abuse

*Safety aspects concerning female subjects of childbearing potential*

**JTA- KOA1 - Clinical Study Protocol**

JTA-KOA1-CSP	V 04	Author: EB	Date: May 10, 2017	Pg. 42/114
--------------	------	------------	--------------------	------------

- Females who are pregnant, lactating or woman with childbearing potential (last menstrual bleeding less than 12 months ago) unwilling to use medically acceptable contraception, or women with childbearing potential unwilling to perform a pregnancy test before administration of study treatment.

*Other exclusion criteria*

- Body Mass Index (BMI) of 35 kg/m^2 or greater

**JTA- KOA1 - Clinical Study Protocol**

JTA-KOA1-CSP	V 04	Author: EB	Date: May 10, 2017	Pg. 43/114
--------------	------	------------	--------------------	------------

**3.7 General Overview of Visits and Procedures**

An overview of the study assessments and procedures is given in Table 1 below. Study procedures are described for JTA-004 products and reference.

**JTA-KOA1 - Clinical Study Protocol**

JTA-KOA1-CSP	V 04	Author: EB	Date: May 10, 2017	Pg. 44/114
--------------	------	------------	--------------------	------------

*Table 1: Detailed Schedule of Visits and Procedures – Double-blind phase*

A large black rectangular redaction box covers the entire content area of the page, obscuring the detailed schedule of visits and procedures mentioned in the caption above.

---

A black rectangular redaction box is located at the bottom of the page, below the horizontal line.

**JTA-KOA1 - Clinical Study Protocol**

JTA-KOA1-CSP	V 04	Author: EB	Date: May 10, 2017	Pg. 45/114
--------------	------	------------	--------------------	------------

**4 DETAILED SCHEDULE OF VISITS AND PROCEDURES**

Before any study-related procedure, the Principal Investigator (or a member of his/her team) will give, both in oral and written, detailed and comprehensive information regarding all aspects of the trial to the patient (including the Patient Information Sheet and ICF). After signing the ICF, the patient will be given a unique Patient Identification Number.

